1.4 Analysis Populations

1.4.1 Intent to Treat (ITT) Population

[REDACTED]

1.4.2 As-Treated (AT) Population

[REDACTED]

1.5 Sample Size Calculations

All sample size calculations were performed using NCSS PASS 11 (Hintze, J., 2011, NCSS, LLC. Kaysville, Utah), unless otherwise specified.

1.5.1 Primary Endpoints

The two primary endpoints will be independently tested. [REDACTED]

[REDACTED]

[REDACTED]

[REDACTED]

[REDACTED]

[REDACTED]

[REDACTED]

[REDACTED]

The power calculation for the primary endpoint of TLF at 30 days is based on the following assumptions:

- [REDACTED]
- One-sided alpha: 2.5%
 - Non-inferiority margin (Δ_{TLF}): 2.9%
 - Randomization ratio (ABSORB IV): 1 (Absorb BVS arm) : 1 (XIENCE arm)

[REDACTED]

With the effective sample size 2574 (Absorb: 1287, XIENCE: 1287) at 30 days, the study has approximately 92% power to demonstrate non-inferiority of Absorb BVS to XIENCE using Farrington and Manning test.

[REDACTED]

[REDACTED]

[REDACTED]

[REDACTED]

[REDACTED]

1.5.2 Powered Secondary Endpoints

1.5.2.1 Powered Secondary Endpoint #1: TLF through 1 year

The TLF at 1 year will be tested for non-inferiority. This analysis will include ~2600 subjects in ABSORB IV.

The hypothesis test is designed to show non-inferiority of Absorb BVS to XIENCE for the TLF at 1 year with a one-sided alpha of 0.025.

The power calculation for the primary endpoint of TLF at 1 year is based on the following assumptions:

- One-sided alpha: 2.5%
- Non-inferiority margin (Δ_{TLF}): 4.8%
- Randomization ratio (ABSORB IV): 1 (Absorb BVS arm) : 1 (XIENCE arm)

With the effective sample size 2470 (Absorb: 1235, XIENCE: 1235) at 1 year, the study has approximately 98% power to demonstrate non-inferiority of Absorb BVS to XIENCE using Farrington and Manning test.

1.5.2.2 Powered Secondary Endpoint #2: Angina through 1 year

[REDACTED]

[REDACTED]

The hypothesis test is designed to show non-inferiority of Absorb BVS to XIENCE for angina within 1 year with a one-sided alpha of 0.025. [REDACTED]

[REDACTED]

[REDACTED]

[REDACTED]

[REDACTED]

The power calculation for the powered secondary endpoint of angina within 1 year is based on the following assumptions:

[REDACTED]

- One-sided alpha: 2.5%
- Non-inferiority margin (Δ_{ANGINA}): 7%
- Randomization ratio (ABSORB IV): 1 (Absorb BVS arm) : 1 (XIENCE arm)

[REDACTED]

With the effective sample size 2470 (Absorb: 1235, XIENCE: 1235) at 1 year, the study has approximately 99% power to demonstrate non-inferiority of Absorb BVS to XIENCE using Farrington and Manning test¹.

[REDACTED]

[REDACTED]

[REDACTED]

[REDACTED]

[REDACTED]

[REDACTED]

[REDACTED]

[REDACTED]

[REDACTED]

[REDACTED]

[REDACTED]

[REDACTED]

1.6 Randomization and Blinding

1.6.1 Randomization

[REDACTED]

[REDACTED]

[REDACTED]

[REDACTED]

[REDACTED]

[REDACTED]

[REDACTED]

1.6.2 Blinding

[Redacted text block]

[Redacted text block]

[Redacted text block]

[Redacted text block]

2. ANALYSIS CONSIDERATIONS

2.1 Statistical Methods

Baseline demographic, clinical, angiographic, procedural, and device data, and treatment results will be summarized using descriptive summary statistics. All data collected will be summarized overall and by treatment arms for ABSORB IV (N=2600) and the pooled population of ABSORB III primary analysis group and ABSORB IV (N=4600).

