1. INTRODUCTION

The ABSORB III Randomized Controlled Trial (RCT) evaluates the safety and effectiveness of the Abbott Vascular Absorb™ Bioresorbable Vascular Scaffold (BVS) System¹². The Absorb BVS System¹³ will be compared to the commercially approved, control stent XIENCE.

ABSORB III also includes a Lead-In phase and an Imaging Cohort and includes a maximum of 220 sites in the United States and outside the United States. The ABSORB III primary endpoint is target lesion failure (TLF) (cardiac death, target vessel myocardial infarction and ischemia-driven target lesion revascularization) at 1 year.

The Absorb BVS used in the ABSORB III trial is the Absorb BVS System manufactured in Temecula California [Absorb BVS System (mfg TEM)]¹³. Clinical trials in the ABSORB Clinical Program have utilized the Absorb BVS System manufactured in Mountain View California (mfg MTV). The Absorb BVS System (mfg TEM) introduces eight additional sizes to the Absorb BVS System product matrix for ABSORB III (Refer to Table 4.1). Concurrent with the manufacturing site transfer, Abbott Vascular has implemented design and manufacturing enhancements to increase product robustness and product ease of use (Refer to Section 2.1.4.6). Hereinafter, Absorb BVS System (mfg TEM)¹³ will be known as Absorb BVS, unless specified.

ABSORB III is a prospective, randomized (2:1 Absorb BVS to XIENCE), single-blind, multi-center trial, registering approximately 2250 subjects. This is the pivotal trial to support the US PMA approval of Absorb BVS. The primary objective of ABSORB III is to evaluate the safety and effectiveness of the Absorb BVS System compared to the XIENCE in the treatment of subjects with ischemic heart disease caused by up to two *de novo* native coronary artery lesions in separate epicardial vessels. The primary endpoint data from this trial will be based on approximately 2000 subjects and will support label claims of non-inferiority of Absorb BVS as compared to XIENCE in 1-year TLF. The ABSORB III will also include a Lead-In Phase and an Imaging Cohort. The ABSORB III will also support a diabetes indication for Absorb BVS.

Lead-In Phase

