5.2 ABSORB IV Major Secondary Endpoint

- **TLF through 1-year, tested for non-inferiority against the control**
- **ABSORB IV Angina Powered Secondary Endpoint:** The percentage of patients who experienced angina within 1 year, tested first for non-inferiority with reflex to superiority against the control.
 - Angina is defined as any angina or angina equivalent symptoms determined by the physician and/or research coordinator after interview of the patient, and as adjudicated by a clinical events committee (CEC).

- This analysis will exclude angina or angina equivalent symptoms that occurred following the index procedure through hospital discharge or 7 days, whichever occurs first.
- This analysis will consist of ~2600 subjects in ABSORB IV.

5.3 *Additional Secondary Endpoint(s)*

In ABSORB IV the following clinical secondary endpoints will be analyzed for all the ~2600 subjects.

- **Acute Success:** (Combined Clinical/Angiographic Endpoint)
 - Device success (Lesion level analysis)
 - Procedural success (Subject level analysis)
- **Clinical Endpoint** in hospital and at each follow-up point (30, 90, 180, 270 days; 1, 2, 3, 4, 5 years).
 - **Component**
 - Death (Cardiac, Vascular, Non-cardiovascular)
 - Myocardial Infarction
 - Attributable to target vessel (TV-MI)
 - Not attributable to target vessel (NTV-MI)
 - Target Lesion Revascularization (TLR)
 - Ischemia driven TLR (ID-TLR)
 - Non ID TLR (NID-TLR)
 - Target Vessel Revascularization (TVR,)
 - ID TVR
 - Non ID TVR
 - All coronary revascularization
 - **Composite Endpoints**
 - Death/All MI
 - Cardiac Death/All MI

- Cardiac Death/TV-MI/ID-TLR (TLF)
- Cardiac Death/All MI/ID-TLR (MACE)
- Cardiac Death/All MI/ID-TLR/ID-TVR, non TL (Target Vessel Failure, TVF)
- Death/All MI/All revascularization
- **Scaffold-Thrombosis / Stent Thrombosis (per ARC definition)**
 - Timing (acute, sub-acute, late and very late)
 - Evidence (Definite and Probable)
- Rehospitalization
 - Coronary artery disease related
 - Cardiovascular, non-CAD related
 - Non-cardiovascular related
- Repeat coronary arteriography
- TLF through 5 years based on 4600 subjects (2000 primary analysis subjects of ABSORB III and 2600 subjects of ABSORB IV)

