2.1.2 Statistics for Categorical Variables

For categorical variables such as gender, MACE, and TVF, results within treatment arm will be summarized with subject counts and percentages/rates, and where specified in the table mockups, with exact 95% Clopper-Pearson³ confidence intervals. Differences between the two treatment arms, when specified, will be summarized with the difference in percents and the Newcombe⁴ score 95% confidence interval for the difference of two percentages.

For efficacy and safety endpoint(s), relative risks (i.e., the ratio of rates), confidence interval for the relative risks, the difference in rates and the confidence interval for difference in rates (using previously-described formulas), and p-values may also be presented for hypothesis generating purposes. The p-values will be based on either Pearson's Chi-square test or Fisher's exact test by checking the expected frequency for each cell in the 2x2 contingency table against Cochran's rule⁶, i.e., if the expected frequencies for all cells are ≥ 5 , then Pearson's Chi-square test will be used, otherwise Fisher's exact test will be used.

For the determination of event rates at all time points (in-hospital, 30 days, 180 days and 1 to 7 (8/9/10) years), the denominators are defined as below based on the type of events.

- Death/MI/Revascularization (DMR) event

Subjects will be included in the analysis if they either had the DMR event by that time or they did not have the DMR event but had follow-up through that time point. In other words, subjects will be included in a given analysis if it can be determined whether or not the subject would have had the DMR event by the time point.

- Stent/Scaffold Thrombosis, Vascular/Bleeding, CVA, and Angina

Subjects will be included in the analysis if they either had the specific event (for example, for analysis on ST, only ST is considered) by that time or they did not have the event but had follow-up through that time point. In other words, subjects will be included in a given analysis if it can be determined whether or not the subject would have had the event by the time point.

Formulas for calculating confidence intervals for the categorical variables are given below.

1. 100(1- α) % Exact Clopper-Pearson Confidence Interval for A Single Proportion³

$$\text{Lower Confidence Limit} = \frac{x}{x + (n - x + 1)F_{1-\frac{\alpha}{2}}(2(n - x + 1), 2x)}$$

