2.1.3 Survival Analysis

2.1.3.1 General Survival Analysis

Survival analysis will be conducted to analyze time-to-event variables. Subjects without events will be censored at their last known event-free time point. Survival curves will be constructed using Kaplan-Meier estimates. Unadjusted log-rank test results will be displayed for comparison of survival distributions at 30 days, 180 days and 1, 2, 3, 4, 5, 6, 7 (1/8/9/10) years. Similar analyses will be performed for the 3-4/3-5/3-6/3-7 (3-8/3-9/3-10) year landmark endpoints.

Summary tables for safety and efficacy endpoints will include failure rates (Kaplan-Meier estimates), hazard ratios, confidence interval for the hazard ratio, and a p-value. For the primary analysis report, all available data will be used.

[REDACTED]

[REDACTED]

[REDACTED]

[REDACTED]

[REDACTED]

[REDACTED]

[REDACTED]

[REDACTED]

[REDACTED]

[REDACTED]

[REDACTED]

[REDACTED]

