2.2 Subgroups for Analysis

All of the following subgroup analyses are intended for the final product IFU. All data collected will be summarized for ABSORB IV (N=2600) and the pooled population of ABSORB III primary analysis group and ABSORB IV (N=4600).

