2.2.2 Diabetes

Diabetic subgroup analysis will be performed on the ITT population. Baseline demographics, baseline subject characteristics, procedure information, morphology, quantitative coronary angiography, and hierarchical/non-hierarchical adverse event data will be summarized with descriptive statistics. Comparisons will be made between treatment arms within the following subgroups:

- Medication treated diabetes mellitus, defined as subjects treated with oral hypoglycemic agents or insulin,
- Non-medically treated diabetes mellitus
- Insulin-treated diabetes mellitus, defined as subjects treated with insulin,
- Non-insulin treated diabetes mellitus, defined as subjects not dependent on insulin,
- All diabetes mellitus, defined as any diabetics with or without medical treatment
- Non diabetes mellitus.

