2.2.3 Other Subgroups

The following subgroups will be evaluated for the ITT population. The treatment comparisons in these analyses are not powered for hypothesis testing and are not meant for confirmatory inference. Baseline demographics, baseline subject characteristics, procedure information, morphology, quantitative coronary angiography, and hierarchical/non-hierarchical adverse event data will be summarized with descriptive statistics. Comparisons will be made between treatment arms within each of these subgroups.

Ethnicity:

- Non-white
- White

Age:

- Age \geq Median, Age $<$ Median
- Age <45 , ≥ 45 and <55 , ≥ 55 and <65 , ≥ 65 and <80 , and ≥ 80

Number of Target Lesion/Vessel Treated:

- Single target lesion/vessel treated, which includes subjects who had only one target lesion/vessel treated
- Dual target lesion/vessel treated, which includes subjects who had two target lesion/vessel treated
- Three target lesion/vessel treated, which includes subjects who had three target lesion/vessel treated.

Angina Status

- Acute coronary syndrome (unstable angina, NSTEMI, recent STEMI)

- Stable angina or silent ischemia
- Recent STEMI
- NSTEMI
- Unstable Angina
- Stable Angina
- Silent ischemia

Antiplatelet Therapy

- P2Y12 Receptor Inhibitor (Yes/No)
- Clopidogrel or Ticlopidine (Yes/No)
- Prasugrel or Ticagrelor (Yes/No)
- Clopidogrel (Yes/No)
- Ticlopidine (Yes/No)
- Prasugrel (Yes/No)Ticagrelor (Yes/No)

RVD by QCA

- $RVD \geq \text{Median}$, $RVD < \text{Median}$
- Small Vessel ($RVD \geq 2.25 \text{ mm}$, $RVD < 2.25 \text{ mm}$)

Implanted Device Diameter

- Device Diameter 2.5 mm vs. 3.0 mm vs. 3.5 mm

Population

- ABSORB III-like (Yes/No)
- ACS (Yes/No)

Implantation technique

- Compete PSP vs Incomplete PSP
 - The implantation technique used during the index procedure must satisfy all of the following criteria to be considered as complete PSP, otherwise it will be incomplete PSP
 1. Pre-dilatation performed
 2. QCA $RVD \geq 2.25 \text{ mm}$
 3. Post-dilatation performed with pressure $> 16 \text{ atm}$ and nominal scaffold diameter $<$ diameter of post-dilatation balloon \leq nominal scaffold diameter + 0.5 mm
- Each of the three individual component of complete PSP listed above (Yes/No)

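### The readable between-arm methods that would apply to the pooled ABSORB III + IV population (N=4600) have no trial stratum, although ABSORB III was randomized 2:1 and ABSORB IV 1:1

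*SAP*

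**What the plan says.** SAP 2.1 asks for all collected data to be summarized overall and by arm, for ABSORB IV (N=2600) and for "the pooled population of ABSORB III primary analysis group and ABSORB IV (N=4600". SAP 2.2 applies the same two populations to the subgroups and adds: "All of the following subgroup analyses are intended for the final product IFU". SAP 2.2.2 (diabetes) states "Comparisons will be made between treatment arms within the following subgroups", and SAP 2.2.3 (other subgroups) states "Comparisons will be made between treatment arms within each of these subgroups".

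The readable methods for comparing arms are these:
- **Binary outcomes (SAP 2.1.2):** "Differences between the two treatment arms, when specified, will be summarized with the difference in percents", with a Newcombe score interval. Relative risks and a Pearson or Fisher p-value from a single 2x2 table may be added.
- **Time to event (SAP 2.1.3.1):** "Unadjusted log-rank test results will be displayed for comparison of survival distributions", with Kaplan-Meier rates and hazard ratios.
- **Continuous outcomes (SAP 2.1.1):** a two-sample t-test and interval.

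None of these has a trial stratum or covariate.

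On allocation, the ABSORB III Introduction says "ABSORB III is a prospective, randomized (2:1 Absorb BVS to XIENCE), single-blind, multi-center trial, registering approximately 2250 subjects". SAP 1.3 and the ABSORB IV Introduction give 1:1 for ABSORB IV. ABSORB IV protocol 5.3 lists, among additional secondary endpoints, "TLF through 5 years based on 4600 subjects (2000 primary analysis subjects of ABSORB III and 2600 subjects of ABSORB IV".

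**The concern.** Each trial is validly randomized, but the pool is not one randomized experiment. With different allocation ratios, trial membership is associated with arm. If the trials also differ in event risk, a crude pooled contrast mixes the trial difference into the device difference, and a larger sample does not remove it.

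A risk difference between the trials is plausible from their designs:
- ABSORB IV admits NSTEMI within two weeks, and STEMI from more than 72 hours up to two weeks. ABSORB III excludes infarction within 72 hours when cardiac enzymes have not normalized.
- ABSORB IV allows up to three lesions, two per vessel. ABSORB III allows two, in separate vessels.
- ABSORB III excludes thrombus in the target vessel. The ABSORB IV exclusion list has no such item.
- The periprocedural MI and angina definitions differ. The ABSORB IV MI definition is also planned as a secondary analysis of ABSORB III, so MI could be harmonized; case mix could not.

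At stake are the pooled 5-year TLF and the pooled subgroup tables meant for the product IFU. A device difference could be hidden or created, depending on which trial has the higher risk.

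**Working it through.** **Inputs.** ABSORB III primary analysis group 2000 at 2:1 (ABSORB III protocol 1 and 4.1); ABSORB IV 2600 at 1:1 (SAP 1.3). All event risks below are assumptions, because the documents give none by trial.

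**The plan's own figure.** 2000 + 2600 = 4600, as stated.

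**Arm composition.** ABSORB III: 1333.3 Absorb and 666.7 XIENCE. ABSORB IV: 1300 and 1300. Pooled: 2633.3 and 1966.7.
- ABSORB III share of the Absorb arm: 1333.3 / 2633.3 = 0.5063
- ABSORB III share of the XIENCE arm: 666.7 / 1966.7 = 0.3390
- Difference: 0.1673

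**Bias with no device effect.** Crude risk difference = 0.1673 x (p3 - p4), where p3 and p4 are the ABSORB III and ABSORB IV risks. Example with p3 = 13%, p4 = 18%: Absorb 0.5063 x 13 + 0.4937 x 18 = 15.47; XIENCE 0.3390 x 13 + 0.6610 x 18 = 16.31; difference -0.84 points. The factor 0.1673 applies to risk differences only; relative risks are computed directly.

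**Full pool of 4600 only.** Coverage uses a normal-approximation interval in place of Newcombe. Log-rank columns are rejection rates at nominal two-sided 5%, from 10,000 simulated trials per case with exponential times and censoring at 5 years.

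| p3 / p4 (%) | Bias (points) | SE (points) | 95% CI coverage | Crude RR (true 1.00) | Log-rank, unstratified | Log-rank, stratified |
|---|---|---|---|---|---|---|
| 13 / 18 | -0.84 | 1.09 | 88.1% | 0.949 | 12.4% | 5.2% |
| 13 / 16 | -0.50 | 1.06 | 92.4% | 0.967 | 7.8% | 4.8% |
| 14 / 15 | -0.17 | 1.05 | 94.7% | 0.989 | not run | not run |
| 14.5 / 14.5 | 0 | 1.05 | 95.0% | 1.000 | 4.8% | 4.7% |
| 16 / 13 | +0.50 | 1.04 | 92.3% | 1.036 | 7.5% | 4.9% |
| 18 / 13 | +0.84 | 1.07 | 87.8% | 1.057 | 11.5% | 5.3% |

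A separate simulation with p4 = 10% and p3 = 13% or 15% gave crude chi-square type I error of 8.2% and 13.5%; a Cochran-Mantel-Haenszel (CMH) test stratified by trial held about 5.0% in both.

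**Subgroups.** If a subgroup has the overall trial mix, the bias is unchanged but the SE grows by 1/sqrt(fraction).
- 25% of each arm: SE doubles. 3-point gap: 0.50 / 2.12 = 0.24 SE, coverage about 94.3%. 5-point gap: 0.84 / 2.18 = 0.39 SE, coverage about 93.3%.
- 10% of each arm: coverage about 94.7% and 94.3%.

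**Cost of stratifying.** Mantel-Haenszel weights n1 x n0 / (n1 + n0) are 444.4 (ABSORB III) and 650 (ABSORB IV), total 1094.4. The crude pool gives 2633.3 x 1966.7 / 4600 = 1125.8. SE ratio = sqrt(1125.8 / 1094.4) = 1.014. At a common risk of 14.5% the SE goes from 1.049 to 1.064 points.

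**The case against.** The strongest objection is that this is an absence claim about a partly blacked-out plan. SAP 1.3.2.3 ends in redacted blocks, 2.1.3.1 is followed by more, 2.1.4 is wholly redacted, and so is the text between the 2.3 window list and 2.11. ABSORB IV protocol 10.4.11 on pooling shows no text. Reference 7 of the SAP, a method for equivalence with censored data, is cited nowhere in the readable text, so some methods are hidden. This stands: a reader might infer that the plan has no trial stratification, and the documents do not support that. They support only that the readable methods have none.

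Second, SAP 2.1 mainly promises descriptive summaries. Differences appear where specified, in table mock-ups that are not shown, and SAP 2.1.3.1 neither mentions the pool nor names the model behind its hazard ratios. ABSORB IV protocol 10.4.3 limits non-powered secondary endpoints to descriptive summary in the ~2600. This stands for the overall pool, so the point is conditional on those methods being used there. It is weaker for subgroups, where SAP 2.2 names the pool and 2.2.2 and 2.2.3 call for arm comparisons. A descriptive difference carries the same bias as a tested one.

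Third, a reader might carry the full-pool rejection rates over to the IFU subgroup tables. The subgroup arithmetic does not support that: test inflation there is small. The mix also varies by subgroup; three-target-lesion subjects come essentially from ABSORB IV alone.

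Fourth, the pooled 5-year TLF is in the August 2018 protocol, whereas this SAP is based on the March 16, 2017 version. True, but the pool of 4600 is in the SAP itself.

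Finally, reporting ABSORB IV alone and the ABSORB III-like subgroup would help expose a discordant result. Neither corrects the pooled estimate.

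**Conclusion.** The point holds as a cheap improvement. Wherever the readable methods are used for a pooled ABSORB III + IV contrast, the estimate is off-centre if the two trials differ in risk. For the full pool, assumed gaps of 1, 3 and 5 points shift the risk difference by 0.17, 0.50 and 0.84 points. A 1-point gap is practically harmless for coverage, and equal risk gives no bias at all. The gap and its sign are assumptions, so no claim that one device is favoured can be drawn.

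A reader might also infer that the confirmatory results are compromised. They are not: the primary 30-day TLF test and the powered 1-year TLF and angina tests use ABSORB IV alone. SAP 1.5.1 mentions two primary endpoints while 1.3.1 lists one, and long-term outcome is a primary objective, which may tempt a reader to treat the pooled comparison as primary. The readable endpoint lists do not say so; ABSORB IV protocol 5.3 places it among additional secondary endpoints. Confidence is medium because of the redactions.

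**What to change.** State in SAP 2.1.2 and 2.1.3.1 that any between-arm comparison on the pooled ABSORB III + IV population, including the pooled subgroups, is stratified by trial: Mantel-Haenszel risk difference and relative risk with a CMH test for binary outcomes, and stratified log-rank and Cox with trial as stratum for time to event. Show the trial-specific estimates beside each pooled one. If a redacted section already does this, align the readable text with it.

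The cost is SAP wording and a stratification statement in the programs, with no new data. If the trials turn out to have equal risk, the SE is about 1.4% larger. With a common 10% control risk and a true 3-point effect, simulated power is 87.5% stratified against 88.4% crude.

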2.1.1 Statistics for Continuous Variables

For continuous variables (e.g., age, percent diameter stenosis, and lesion length), results within treatment arm will be summarized with the numbers of observations, means, and standard deviations, and in addition, with medians, quartiles, minimums, maximums, and 95% confidence intervals for the means, when specified. Differences between the treatment arms, when specified, will be summarized with the differences of the two means and 95% confidence intervals for the difference between the means, and p-values from t-test may also be presented for hypothesis generating purposes.

Formulas for calculation of the confidence intervals for the continuous variables are given below:

1. 100(1- α)% Confidence Interval For A Single Mean²

$$\bar{x} \pm t_{\frac{\alpha}{2}} \frac{s}{\sqrt{n}}$$

where:

\bar{x} = sample mean

s = sample standard deviation

n = sample size

$t_{\frac{\alpha}{2}}$ = the alpha/2 t - statistic for n – 1 degrees of freedom

2. 100(1- α)% Confidence Interval For The Difference of Two Means Under The Assumption Of Equal Variances Between The Two Groups²

$$(\bar{x}_1 - \bar{x}_2) \pm t_{\frac{\alpha}{2}} \sqrt{s_p^2 \left(\frac{1}{n_1} + \frac{1}{n_2} \right)}$$

where:

\bar{x}_1 = sample mean for group 1

\bar{x}_2 = sample mean for group 2

$$s_p^2 = \frac{(n_1 - 1)s_1^2 + (n_2 - 1)s_2^2}{n_1 + n_2 - 2}$$

s_1 = sample standard deviation for group 1

s_2 = sample standard deviation for group 2

n_1 = sample size for group 1

n_2 = sample size for group 2

$t_{\frac{\alpha}{2}}$ = the alpha/2 t - statistic for $n_1 + n_2 - 2$ degrees of freedom

3. 100(1- α) % Confidence Interval for the Difference of Two Means under the Assumption of Unequal Variances between the Two Groups²

$$(\bar{x}_1 - \bar{x}_2) \pm t_{\frac{\alpha}{2}} SED$$

With the degrees of freedom for the approximate t statistic is determined by Satterthwaite's formula² as follows:

$$df = \frac{(w_1 + w_2)^2}{\frac{w_1^2}{n_1 - 1} + \frac{w_2^2}{n_2 - 1}}$$

where:

\bar{x}_1 = sample mean for group 1

\bar{x}_2 = sample mean for group 2

s_1 = sample standard deviation for group 1

s_2 = sample standard deviation for group 2

n_1 = sample size for group 1

n_2 = sample size for group 2

$$SED = \sqrt{\frac{s_1^2}{n_1} + \frac{s_2^2}{n_2}}$$

$$w_1 = \frac{s_1^2}{n_1}$$

$$w_2 = \frac{s_2^2}{n_2}$$

